10.8.1.2 Secondary Efficacy Analyses

Secondary efficacy analyses will compare the three study arms on the following:

- a. proportion seroconverting one month after the first dose of vaccine, but before the second dose
- b. proportions achieving seroprotection one month after both the first and second doses of vaccine. *Seroprotection* is defined as HI titers of ≥1:40, including among those pre-immune participants with detectable titers before vaccination.

HIRRC/CDC Needle-free Intradermal	Page 100	File: 4785-ID-INF-Prot-Engl-2008Jun24.doc
Influenza Study - CDC-ISO-4785	of 138	2008-Jun-24

- c. geometric mean titers (GMTs) of HI assays performed one month after both doses 1 and 2.
- d. satisfying the clinical criteria of the European guidelines for annual vaccine registration for adults aged 18 to 60 (there are none for children), ^{CPMP1997} that antibody responses to at least one strain of the vaccine achieve:
 - >40% seroconversion among participants
 - >2.5 increase in inverse geometric mean titer from pre-vaccination to final titers (e.g., from inverse GMT of 8 initially to final of ≥20)
 - >70% seroprotection among participants
- e. proportion with prompted and unsolicited adverse events following immunization.

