10.4.2.4 Vaccine Immunogenicity Profile

Substantial clinical experience in use of the current "Triton[®] X-100 split" formulation of Vaxigrip[®] influenza vaccine has accumulated since the early 1990s when it replaced the earlier "Tween-ether split" product, first introduced in France

in 1968. ^{Lina2000, Saliou2005} Hundreds of millions of doses of this current Vaxigrip[®] formulation have been distributed and used worldwide over many seasons with, of course, the annual modifications of virus strain composition.

The immunogenicity of Vaxigrip[®] has been demonstrated in clinical trials in adults from age 18 to 60 years, in the elderly over 60 years, and in children from 6-36 months and from 3-10 years. Annual studies in adults are performed to verify the immunogenicity of annual changes in strain composition (data on file at Aventis Pasteur S.A., Lyon France ^{AventisPasteur2005}) In the unpublished *Annual Study* (see Figure 5), and in *Study 3 (35)*, ^{Lina2000} a single dose was given and antibody titers were assessed immediately before vaccination and then 21 days later. In *Study 2 (36)* ^{Gonzalez2000} antibody titers were assessed immediately before the first dose and 27-33 days following the second vaccine dose.

Figure 5. Table 3 from the Vaxigrip[®] monograph AventisPasteur2005

references: (13) = "data on file", (35) = Lina2000, (36) = Gonzalez2000

Study #	Trial design	Dosage, route of administration and duration	Study subjects (n=number)	Mean age (Range)	Gender
Annual Study (13)	Open	0.5 mL IM	>50 >50	18-60 years >60 years	
Study 2 (13) (36)	Open	0.25 mL IM; 2 doses 1 month apart	65	6 months to 3 years	Male 37 Female 28
Study 3 (35)	Open	0.5 mL	42 (12 had received prior influenza vaccination)	8-10 years	Male 19, Female 23

The results of these studies are quoted verbatim from the product monograph AventisPasteur2005.

"The efficacy of influenza vaccine is assessed using a surrogate for protection defined as the immune response elicited by the vaccine (hemagglutination inhibition). In the annual studies, the serologic responses of both adult age groups to all antigens must meet the assessment criteria as defined in the European Requirements for Influenza Vaccines (i.e., for subjects 18-60 years – at least one of seroconversion or significant increase in antihemagglutinin antibody titre in >40%, mean GMT increase >2.5, proportion of subjects achieving HI titre or seroprotection >70%, and for

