10.8.2 Determination of Sample Size

The total participants of the combined phases I and II (N=450), results from 150 participants in each of three study arms. This number results from rounding up, in anticipation of an estimated 5% loss-to-followup, from a calculated 142 participants (*non-inferiority* model ^{FDA1998, Chow2002}) or 139 participants (*superiority* model) required per arm, derived using PASS 2002TM software (Number Cruncher Statistical Systems, Kaysville, UT, http://www.ncss.com),^{Hintze2005} as follows:

The full-dose, standard IM route control arm of the study (IM-NS-0.25) is assumed to achieve the mean seroconversion rate against the A/H1N1 strain (86.4%) demonstrated in 1 published ^{Gonzales2000} (76%) and 3 unpublished ^{Saliou2005} recent clinical trials (~88%, ~79%, ~97%) of Vaxigrip® influenza vaccine (Sanofi-Pasteur, Lyon, France) conducted among a similar age range (6-35 months) of children as those to be studied in this trial (6-24 months). (Immunogenicity for at least one strain satisfies European Committee for Proprietary Medicinal Product requirements for European registration. ^{CPMP1997}) This rate is somewhat lower but consistent with the 91% seroconversion reported after use of a different influenza vaccine, Fluzone®, manufactured by the same company at its Swiftwater, PA, USA plant. ^{SanofiPasteur2004, Hoberman2003}

Based on prior literature indicating equivalent serologic responses between standard, full-dose, needle-syringe influenza vaccination and (1) reduced-dose, needle-syringe intradermal (ID) vaccination (see section 9.4.2), as well as (2) reduced-dose jet injected (JI) ID vaccination (see section 9.4.4), the same 86.4% seroconversion rate is postulated for the investigational intradermal study arm.

There is a paucity of and some conflicting results among clinical trials of reduced-dose influenza vaccination comparing the same antigen dosage by the ID versus IM or SC routes (see section 9.4.3). Dose-sparing trials without an ID arm showed a small decrement in response, ^{Treanor2002} so reduced dosage via the standard IM route is suggested as a useful strategy in time of shortage. ^{Treanor2004} Others have called for careful clinical trials to confirm the effect of the ID route. ^{LaMontagne2004} To fulfill this call

HIRRC/CDC Needle-free Intradermal	Page 101	File: 4785-ID-INF-Prot-Engl-2008Jun24.doc
Influenza Study - CDC-ISO-4785	of 138	2008-Jun-24

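### Secondary analysis 10.8.1.2(d) lets one strain satisfy the European immunogenicity criteria, whereas the protocol's own quotation of those criteria in 10.4.2.4 requires every strain to qualify

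*Protocol*

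**What the plan says.** Three places in the protocol describe the same European criteria, and all cite CPMP 1997.

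- **10.8.1.2, item d (the rule to be applied).** Using the adult 18-to-60 criteria, because none exist for children, the analysis asks "that antibody responses to at least one strain of the vaccine achieve" a list of three thresholds. The first is ">40% seroconversion among participants"; the others are a GMT increase above 2.5 and seroprotection above 70%. No word says whether one bullet or all three are needed. The worked example for the GMT bullet runs from 8 to a final value of 20 or more.
- **10.8.2 (sample size).** A parenthesis beside the choice of the A/H1N1 planning rate states: "Immunogenicity for at least one strain satisfies European Committee for Proprietary Medicinal Product requirements for European registration".
- **10.4.2.4 (vaccine immunogenicity profile).** The quoted product monograph says that "the serologic responses of both adult age groups to all antigens must meet the assessment criteria". For ages 18 to 60 it requires "at least one of seroconversion or significant increase in antihemagglutinin antibody titre in >40%, mean GMT increase >2.5", with seroprotection above 70% as the third alternative.

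**The concern.** Between 10.4.2.4 and 10.8.1.2 the phrase *at least one* has moved from the thresholds to the strains. In the quoted rule every strain must qualify and a strain may do so by any one of three routes. In item d a single strain is enough. Both cannot describe the same guideline.

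Item d is the only secondary efficacy analysis with absolute pass or fail thresholds; the primary rule in 10.8.1.1 is relative to control. Sections 9.6.2 and 9.6.3 address the results to officials planning for vaccine shortage. A statement that a reduced-dose arm satisfied the European criteria could be made on the best of three strains, against the protocol's own account of what those criteria ask.

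**Working it through.** **1. Does any stated figure depend on item d?** No. The nearest is the 142 per arm in 10.8.2. With both rates 0.864, margin 0.104, one-sided alpha 0.05 and power 0.80, the Farrington-Manning score formula, using constrained null rates 0.797 and 0.901, gives

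n = [(1.645 × 0.501 + 0.842 × 0.485) / 0.104]² ≈ 140.4, so 141 (stated 142).

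Here 0.501 = √(0.797 × 0.203 + 0.901 × 0.099) and 0.485 = √(2 × 0.864 × 0.136). Allowing 5% loss, 142 / 0.95 = 149.5, so 150. Item d enters neither step.

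**2. The rules side by side.**

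| | Strains needed | Thresholds needed per strain |
|---|---|---|
| 10.4.2.4 | all three | any one of three |
| 10.8.1.2(d), bullets as alternatives | one | any one of three |
| 10.8.1.2(d), bullets as joint | one | all three |

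No reading of item d yields each strain.

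**3. A hypothetical arm that separates them.** H1N1: seroconversion 80%, GMT ratio 10, seroprotection 80%. H3N2 and B: 25%, 2.0 and 40%. Item d is met on either reading, through H1N1. The 10.4.2.4 rule fails on two of three strains.

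**4. Size, on seroconversion alone.** Take n = 142 per arm. Exceeding 40% needs more than 0.4 × 142 = 56.8, so at least 57 responders. For each strain P = Pr(X ≥ 57), with X binomial(142, p). Treating strains as independent for simplicity, the one-strain rule passes with probability 1 − Π(1 − P) and the every-strain rule with ΠP.

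| True rates | P by strain | One strain | Every strain |
|---|---|---|---|
| 86.4 / 85.2 / 56.0% (historical means, 10.4.2.4) | 1.000, 1.000, 0.9999 | 1.00 | 1.00 |
| 86.4 / 85.2 / 30% | 1.000, 1.000, 0.0064 | 1.00 | 0.006 |
| 86.4 / 30 / 30% | 1.000, 0.0064, 0.0064 | 1.00 | 0.00 |
| 50 / 20 / 20% | 0.9927, 0.0000, 0.0000 | 0.99 | 0.00 |

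The 20%, 30% and 50% rates are assumptions for illustration. The calculation omits GMT increase and seroprotection, for which the protocol gives no planning rates. These are further routes for a strain to qualify, so the table overstates how often the rules would part.

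**5. The trial data in 10.4.2.4.** In the published study at 6 months to 3 years, every strain exceeds all three thresholds (lowest seroconversion 61.2%, lowest seroprotection 81.6%, lowest GMT increase 4.1). In the study at 8 to 10 years, the B strain has seroconversion 29% and GMT increase 2.3 but seroprotection 100%, so it qualifies by one route. Both studies pass both rules.

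**6. The worked example.** 20 / 8 = 2.5, which does not exceed 2.5. A final GMT of exactly 20 is admitted by the example and excluded by the threshold.

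**The case against.** The strongest reply is that little turns on item d. It is one of five secondary items. An arm becomes acceptable only through the non-inferiority comparison in 10.8.1.1, made for each strain. No phase II criterion or stopping rule uses item d, its ingredients are already study variables, and either rule can be applied to the same data. All of this stands and limits the weight of the point.

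Four stronger readings are tempting, and the documents do not support them.

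- **That one strain carrying the claim is already likely with this injector.** A reader might take this from the frail-elderly trial in 10.4.3.6.3, where intradermal GMTs were 50.7, 14.1 and 23.3. Low seroprotection does not fail a strain under the 10.4.2.4 rule, because it is one of three routes. The same paragraph reports that 31 of 45 intradermal recipients (69%) had a four-fold rise or a titre of at least 40 to all three antigens. That population was also elderly, for whom 10.4.2.4 gives other thresholds.
- **That item d can err in both directions.** An arm that meets the quoted rule would fail item d only if the three bullets were joint, which item d does not state. That is an ambiguity to remove, not a demonstrated second error.
- **That the guideline itself is shown to be misquoted.** The guideline is not at hand. The monograph text is the manufacturer's account of its annual adult studies. The documents show that the protocol disagrees with itself.
- **That the sample size rests on the one-strain rule.** The parenthesis stands beside the choice of the A/H1N1 rate, but 10.8.2 does not derive that choice from it, and the arithmetic does not use it.

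**Conclusion.** The contradiction is real and internal. Item d and the parenthesis in 10.8.2 let one strain suffice, while the protocol's only fuller account of the same criteria requires all. This is a wrongly stated rule, not detail left to a later analysis plan.

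Its reach is limited to a secondary benchmark borrowed from adults. At the historical seroconversion rates both rules pass with probability about 1.00. They diverge only if strains respond unevenly, for example about 1.00 against 0.006 when one strain's true seroconversion is an assumed 30% and the other routes are ignored. A reader might infer that the trial's main conclusion is at risk; it is not. The correction is worth making, but nothing in the primary analysis or design waits on it.

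**What to change.** - Reword 10.8.1.2(d) to: *for each of the three vaccine strains, at least one of: seroconversion >40%; GMT ratio >2.5; seroprotection >70%*, with results reported by strain and arm. This settles both the strain count and the status of the three bullets.
- Correct or delete the one-strain parenthesis in 10.8.2.
- Change the worked example to a final GMT above 20.

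The sponsor holds the cited guideline and should check the new wording against it, ideally before unblinding. The change costs wording only: no data, assay or computation is added. The downside is a stricter claim across strains, since a weak strain can no longer be covered by a strong one.

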10.8.2 Determination of Sample Size

The total participants of the combined phases I and II (N=450), results from 150 participants in each of three study arms. This number results from rounding up, in anticipation of an estimated 5% loss-to-followup, from a calculated 142 participants (*non-inferiority* model ^{FDA1998, Chow2002}) or 139 participants (*superiority* model) required per arm, derived using PASS 2002TM software (Number Cruncher Statistical Systems, Kaysville, UT, http://www.ncss.com),^{Hintze2005} as follows:

The full-dose, standard IM route control arm of the study (IM-NS-0.25) is assumed to achieve the mean seroconversion rate against the A/H1N1 strain (86.4%) demonstrated in 1 published ^{Gonzales2000} (76%) and 3 unpublished ^{Saliou2005} recent clinical trials (~88%, ~79%, ~97%) of Vaxigrip® influenza vaccine (Sanofi-Pasteur, Lyon, France) conducted among a similar age range (6-35 months) of children as those to be studied in this trial (6-24 months). (Immunogenicity for at least one strain satisfies European Committee for Proprietary Medicinal Product requirements for European registration. ^{CPMP1997}) This rate is somewhat lower but consistent with the 91% seroconversion reported after use of a different influenza vaccine, Fluzone®, manufactured by the same company at its Swiftwater, PA, USA plant. ^{SanofiPasteur2004, Hoberman2003}

Based on prior literature indicating equivalent serologic responses between standard, full-dose, needle-syringe influenza vaccination and (1) reduced-dose, needle-syringe intradermal (ID) vaccination (see section 9.4.2), as well as (2) reduced-dose jet injected (JI) ID vaccination (see section 9.4.4), the same 86.4% seroconversion rate is postulated for the investigational intradermal study arm.

There is a paucity of and some conflicting results among clinical trials of reduced-dose influenza vaccination comparing the same antigen dosage by the ID versus IM or SC routes (see section 9.4.3). Dose-sparing trials without an ID arm showed a small decrement in response, ^{Treanor2002} so reduced dosage via the standard IM route is suggested as a useful strategy in time of shortage. ^{Treanor2004} Others have called for careful clinical trials to confirm the effect of the ID route. ^{LaMontagne2004} To fulfill this call

HIRRC/CDC Needle-free Intradermal	Page 101	File: 4785-ID-INF-Prot-Engl-2008Jun24.doc
Influenza Study - CDC-ISO-4785	of 138	2008-Jun-24

and clarify the issue, the reduced-dose IM arm is included in this trial with the same statistical assumptions as per the ID arm.

Applying a *non-inferiority* model using a score test for two independent proportions, ^{Farrington1990} a margin around these expected seroconversion rates (0.864) of twelve percent is selected, i.e., 0.104. This corresponds to an *acceptable* seroconversion rate as low as 0.760 (76.0%) in the investigational study arms, to demonstrate that the investigational arms are not worse than the control arm by more than this amount. (Decrements of up to 15% are suggested for non-inferiority trials in which the standard treatment rate is between 80% and 90%.^{Chow2003}) Model parameters were set at:

target
$$\alpha = 0.05$$

Power = $0.80 \ (\beta = 0.2)$

Standard group proportion (P2) = 0.864 (from prior studies) Actual experimental group proportion (P1.1) = 0.864 (anticipated) Equivalent experimental group proportion (P1.0) = 0.760 (lowest acceptable) Equivalent margin difference (D0) = -0.104 (acceptable twelve percent decrement) Actual margin difference (D1) = -0.104 (acceptable twelve percent decrement) Experimental group sample size (N1) = 142 Standard (control) group sample size (N2) = 142

The null hypothesis H_0 is that the seroconversion rate for the treatment arm is at least 12% lower than for the standard arm, and that under the alternative hypothesis H_a , the difference in seroconversion rates between the treatment and standard arms is less than 12% (i.e., the treatment is not inferior to standard). If the study rejects the null hypothesis H_0 and accepts the alternative H_a , we may conclude that the treatment is not inferior to standard, with only a 0.05 probability of reaching this conclusion due to random error.

Applying an alternative *superiority* model for two independent proportions (null case) using a one-sided Z test with pooled variance, ^{Chow2003} a sample size of 139 or greater in each group will detect with 80% power ($\beta = 0.2$) a superiority of ten percent or greater (seroconversion \geq 95%) for either of the investigational study arms over the control arm (assumed 86.4%). As for the non-inferiority model, above, the significance level of the test was targeted at $\alpha = 0.05$.

10.8.3 Randomization

As detailed in section 10.4.4, participants will be allocated to one of the three treatment groups (ID-JI-0.1, IM-NS-0.1, IM-NS-0.25) by a random allocation method not subject to observer choice or whim. Participants will be enrolled in blocks of six, each containing two members of each of the three treatment groups, in random order. One

HIRRC/CDC Needle-free Intradermal	Page 102	File: 4785-ID-INF-Prot-Engl-2008Jun24.doc
Influenza Study - CDC-ISO-4785	of 138	2008-Jun-24

block will be randomly split between the first and last enrollees in the study, to prevent block counting.

10.9 Stopping Rules to Suspend Vaccination

10.9.1 Phase I

During phase I (n=48), upon the occurrence of *Serious Adverse Events* in three (3 [6%]) or more enrolled vaccinees, or incidents of *entire-limb swelling*^{Rennels2000} or other *severe local reactions* at the **INF** injection site in five (5 [10%]) or more vaccinees, which, in the opinion of any of the Principal or Senior Dominican or U.S. Investigators are *possibly-related* or *probably-related* to the investigational vaccination (see section 10.5.2.2 for definitions).

Further **INF** vaccination for all participants will be suspended immediately until review of the data by the DSMB. Upon analysis using unblinded access to the study group code allocations, the DSMB shall provide either its clearance to resume vaccination, with restrictions, if any, as appropriate, or its denial to proceed. (The IRBs will be contemporaneously informed of any such suspension, as well as the outcome of the DSMB review, and the investigators will adhere to any resulting IRB guidance.)

10.9.2 Phase II

In accordance with the same criteria and procedures as described for Phase I in section 10.9.1 above, in phase II (n=402), all vaccination shall be suspended, upon the occurrence of *possibly-related* or *probably-related Serious Adverse Events* in sixteen (16 [4%]) or more vaccinees, or *possibly-related* or *probably-related entire-limb swelling* or other *severe local reactions* at the INF injection site in twenty (20 [5%]) or more vaccinees.

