Serum and Virus Collection (§10.6.10): Blood specimens to measure serologic responses will be collected three times, just prior to vaccination on day 0 (INF dose 1), on day 28 (INF dose 2), and on day 56 (INF "insurance" dose 3). Participants with influenza-like illness will have nasopharyngeal/throat swabs analyzed by rapid influenza test. Those with positive influenza A results will have specimens sent for viral culture.

Stopping rules (§10.9): Vaccination will be suspended for all participants, pending unblinded review by the DSMB and its clearance or denial to resume, as well as simultaneous IRB guidance, upon occurrences deemed *possibly-* or *probably-related* to the study vaccinations by any of the Dominican or U.S. Principal or Senior Investigators of *serious adverse events* in any 3 (6%) phase I vaccinees or any 16 (4%) phase II vaccinees, or upon incidents of *entire-limb swelling* or other *severe local reactions* at the **INF** injection site in any 5 (10%) phase I vaccinees or any 20 (5%) phase II vaccinees.

Criteria for proceeding to phase II (§10.10): Either or both of the study's investigational arms (**ID-JI-0.1** or **IM-NS-0.1**) will not proceed to phase II if the observed frequency of the following events in that arm exceeds the frequency observed in the control **IM-NS-0.25** group by the designated excess: (Invest. Arm) – (Control Arm)

-	· · · · · · · · · · · · · · · · · · ·	
•	Any serious adverse event, possibly- or probably-related:	exceeds by ≥ 3
•	Fever >40° C possibly- or probably-related:	exceeds by ≥4
•	Injection site whole-limb swelling:	exceeds by ≥4
•	Injection site induration >5 cm diameter:	exceeds by ≥ 5
•	Injection site erythema >5 cm diameter:	exceeds by ≥ 5
•	Injection site pain level 3 (cries upon moving limb):	exceeds by ≥ 5

Number of participants planned:

Phase I = 48; phase II = 402 (total participants = 450)

Participant characteristics and main criteria for inclusion and exclusion (§10.3):

Healthy, full-term infants of age ≥ 6 -to- <24 months (before second birthday) who are recruited as prior or current patients, or siblings of patients, attending a public outpatient clinic at the national children's hospital. Excluded will be infants not up-to-date on immunizations who need other injected vaccines recommended routinely at younger ages, or

HIRRC/CDC Needle-free Intradermal	Page 6	File: 4785-ID-INF-Prot-Engl-2008Jun24.doc
Influenza Study - CDC-ISO-4785	of 138	2008-Jun-24

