10.10 Criteria for Proceeding to Phase II

Upon unblinded analysis by the DSMB (see section 10.11) of the results of the phase I study, the observed adverse reactions will be tallied by the DSMB for each of the study arms (control IM-NS-0.25, investigational IM-NS-0.1 and ID-JI-0.1). Either or both investigational study arm(s) for which an observed numbers of reactions exceeds the number observed in the IM-NS-0.25 control arm by the following degree for any reactions listed will be eliminated from the phase II study. If both investigational arms are thus eliminated, the study will not proceed to phase II.

	Excess = no. in investigational arm less no. in control arm
Serious Adverse Reaction, possibly- or probably-related	≥3
Fever >40° C, possibly- or probably-related	≥4
Injection site whole-limb swelling	≥4

HIRRC/CDC Needle-free Intradermal	Page 103	File: 4785-ID-INF-Prot-Engl-2008Jun24.doc
Influenza Study - CDC-ISO-4785	of 138	2008-Jun-24

Injection site induration >5 cm in diameter	≥5
Injection site erythema >5 cm in diameter	≥5
Injection site pain level 3 (cries upon moving limb)	≥5

For example, if four (4) children in the IM-NS-0.25 control arm experience inducation of >5 cm, eight (8) do so from the IM-NS-0.1 arm, and nine (9) from the ID-JI-0.1 arm, then the IM-NS-0.1 study arm may proceed to phase II, but the ID-JI-0.1 arm will be dropped from phase II.

Based upon this analysis and any other relevant information, the DSMB will decide whether or not the study should proceed to phase II as designed, should be modified and then proceed, or should be terminated. This decision shall be duly informed to the investigators, without revealing unblinded information nor study-group-specific analyses. Regardless of a DSMB decision permitting phase II, the study sponsor may elect for any reason not to proceed, and to terminate the study after phase I.

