The investigational spacer to be studied in this trial has already been subjected to a number of well-conducted studies on adults without serious adverse consequences (see section 10.4.3.6). Thus, it is reasonable now to study young children in order to gather essential data for policymaking on how such participants may be protected in the event of pandemic. This study is phased with conservative stopping rules that can quickly respond to any clinical outcomes suggesting untoward risks to these children.

12.2 Why is this study being done in the Dominican Republic and not in the United States or Europe, where its sponsor and principal parties are based?

This kind of study could and should very well be conducted in the U.S. or Europe, as the questions it poses are relevant to those geographic areas as well. However, the collaboration supporting this study benefits from the technical scientific and/or financial contributions of WHO and PATH, organizations with primary missions to seek answers to the health problems of the developing world. This global perspective is also within the mission of CDC, which recognizes that national health and security depends on the health and security of all nations. The selection of the HIRRC as a partner in this study resulted from its excellent track record of clinical trials of vaccines and antimicrobials (see section 10.2.1).

HIRRC/CDC Needle-free Intradermal	Page 112	File: 4785-ID-INF-Prot-Engl-2008Jun24.doc
Influenza Study - CDC-ISO-4785	of 138	2008-Jun-24

12.3 Why is the study planning to use Vaxigrip[®] instead of an influenza vaccine licensed in the U.S.A.?

The brand of influenza vaccine to use in this study was selected by a process of elimination from among the seven major products on the international market, of which three are now sold in the U.S.

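### The phase II suspension counts of 16 (4%) and 20 (5%) fit only a three-arm phase II of about 402 children, and nothing restates them if section 10.10 removes an arm

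*Protocol*

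**What the plan says.** Section 10.9.2 applies the phase I criteria and procedures to phase II: "in phase II (n=402), all vaccination shall be suspended" when possibly or probably related serious adverse events (SAEs) occur "in sixteen (16 [4%]) or more vaccinees", or when possibly or probably related entire-limb swelling or other severe local reactions occur "in twenty (20 [5%]) or more vaccinees". The synopsis gives the same SAE rule: "in any 3 (6%) phase I vaccinees or any 16 (4%) phase II vaccinees". Events are counted cumulatively and pooled over arms.

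Phase I (section 10.9.1, n=48) is built the same way, with suspension at SAEs in "three (3 [6%]) or more enrolled vaccinees", or at five (10%) for the local reactions.

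Section 10.10 compares each investigational arm with control after phase I. An arm over any listed limit "will be eliminated from the phase II study". The section's worked example ends with one arm going forward and the other dropped. Neither section 10.9.2 nor section 10.10 says what then happens to the counts.

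Section 12.1 describes the safeguards as follows: "This study is phased with conservative stopping rules that can quickly respond to any clinical outcomes suggesting untoward risks to these children".

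**The concern.** A suspension rule printed as both a count and a percentage is clear only while the two agree. Here they agree for full three-arm enrolment, and the protocol itself provides for a phase II with fewer arms. In that branch a reader cannot tell whether 16 or 4% (or 20 or 5%) is the rule. If it is the count, the rule is looser than its label throughout phase II.

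A second, lesser difficulty is that the rule has no interim denominator. Suspension protects children not yet vaccinated, but a count sized for the end of enrolment acts late when events are frequent early. That sits poorly with the section 12.1 description of rules that respond quickly. At stake is the only automatic suspension in phase II, for intradermal jet injection of influenza vaccine, on which section 9.6.2 says there are no data at this age.

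**Working it through.** **Inputs.** Counts 16 and 20, labels 4% and 5%, and n=402 (section 10.9.2); 134 per arm (section 10.1.2); possible removal of an arm (section 10.10). Assumed here: 134 per arm is kept if an arm is dropped; children are independent with one constant event rate; each child is counted once.

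**1. Reproduce the printed percentages.**
- 16/402 = 3.98%, and 4% × 402 = 16.08.
- 20/402 = 4.98%, and 5% × 402 = 20.1.

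Both are correct for 3 × 134 = 402. To the nearest whole percent, 16 reads as 4% from n = 356 (16/356 = 4.49%) and 20 reads as 5% from n = 364 (20/364 = 5.49%).

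**2. Remove one arm.** 2 × 134 = 268.
- 16/268 = 5.97%; 20/268 = 7.46%.
- 4% × 268 = 10.7 children; 5% × 268 = 13.4 children.

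Because 268 is below both 356 and 364, neither label is right at any stage of a two-arm phase II, even to rounding.

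**3. Chance of ever reaching the count**, from the exact binomial tail P(X ≥ r) with X ~ Binomial(n, p):

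| Trigger | True rate | n = 402 | n = 268 |
|---|---|---|---|
| Related SAEs, r = 16 | 4% | 0.543 | 0.074 |
| Severe local reactions, r = 20 | 5% | 0.541 | 0.050 |

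**4. Behaviour during accrual.** Observed rate at which the count is first met, r/n:

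| Children vaccinated in phase II | 16/n | 20/n |
|---|---|---|
| 100 | 16.0% | 20.0% |
| 201 | 8.0% | 10.0% |
| 268 | 6.0% | 7.5% |
| 402 | 4.0% | 5.0% |

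So 15 related SAEs among the first 100 children (15.0%), or 19 severe local reactions (19.0%), would not trigger mandatory suspension. At true rates of twice the label:
- SAEs at 8%: P(16 or more) is 0.006 by child 100 and 0.54 by child 200. The 16th event is expected at 16/0.08 = 200 children.
- Local reactions at 10%: P(20 or more) is 0.002 by child 100 and 0.53 by child 200. The 20th event is expected at 20/0.10 = 200 children.

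**The case against.** The strongest reply is that nothing is miscalculated. Section 10.9.2 names n=402 in the same sentence, the operative rule is a count, and the percentage only labels it. Phase I uses the same construction. This stands for the planned three arms. A reader might infer that the percentages are wrong at every point before child 402. They are not: to rounding they hold from about child 356 and child 364.

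A reader might also infer that vaccination would simply continue through high event rates. The documents do not support that.
- Every SAE reaches the U.S. principal investigator within 24 hours (section 10.5.2.2.5).
- Section 10.12 requires prompt reporting to the DSMB and both IRBs of unanticipated related SAEs, of SAEs running above expectation, and of certain unanticipated events of any severity. Section 10.5.2.2.1 counts an unexpected frequency as unanticipated, so an excess of severe local reactions can come within it.
- Section 10.11 lets the DSMB meet on its own initiative.

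What remains is that none of these is an automatic suspension, and none of the four meetings listed in section 10.11 falls within phase II accrual.

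On the dropped arm, 268 is an assumption, and section 10.10 lets the DSMB modify the study before phase II. The arm that exceeded the limits would also be gone. But permission to modify is not an instruction to restate the counts.

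Finally, the apparent remedy, a running percentage, has a real price. As an illustration, a 4% running share applied from child 48 to child 402 would suspend about 35% of trials at a true 2% rate, against 0.8% under the count of 16. The early silence is therefore partly a trade-off, and it is for the sponsor and DSMB to weigh.

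**Conclusion.** The concern holds in limited form. The counts are correct for about 402 children in three arms. They are not reconciled with section 10.10, which requires removal of an arm in defined circumstances. With 134 per arm kept, the triggers sit at 6.0% and 7.5% instead of 4% and 5%, and the chance of ever reaching them at the printed rates falls from 0.54 to 0.07 and from 0.54 to 0.05. These probabilities rest on independent children, a constant rate and the assumed 268.

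The accrual point is secondary. The mandatory rule can stay silent at observed rates several times its labels, which fits poorly with section 12.1, but discretionary review remains available. The documents do not show an arithmetic error, an absence of other safeguards, or that any particular threshold is the right one.

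**What to change.** Reconcile section 10.9.2 and the synopsis with sections 10.10 and 12.1:
- state whether the count or the percentage governs phase II suspension;
- restate the counts, or the percentages printed beside them, for a phase II with one investigational arm removed;
- have the sponsor and DSMB decide the levels and what, if anything, applies during accrual, and bring the section 12.1 description into line with that decision.

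No threshold and no running-percentage rule is proposed here. The cost is a few sentences in the protocol and synopsis, agreed with the DSMB and handled under the amendment procedure in section 10.13. The planned three-arm rule need not change.
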